3.5. Method of Assigning Subjects to Treatment Groups

This is an open-label, single-arm study. Screening is carried out to enable confirmation of patient eligibility. Eligible patients are administered emapalumab.

3.6. Blinding and Unblinding

Not applicable.

3.7. Schedule of Events

A detailed schedule of events for the study is provided in Table 1 and Table 2 of the protocol.

[figure not shown]
4. Statistical Analysis and Reporting

4.1. Introduction

Data processing, tabulation of descriptive statistics, calculation of inferential statistics, and graphical representations will be performed primarily using SAS (release 9.4 or higher). If the use of other software is warranted, the final statistical methodology report will detail what software was used for what purposes.

Continuous (quantitative) variable summaries will include the number of patients (n) with non-missing values, mean, standard deviation, median, minimum, and maximum. The minimum and maximum will be reported with the same degree of precision (i.e., the same number of decimal places) as the observed data. Mean, standard deviation and median will be reported to 1 degree of precision more than the observed data.

Categorical (qualitative) variable summaries will include the frequency and percentage of patients who are in the particular category or each possible value. In general, the denominator for the percentage calculation will be based upon the total number of patients in the study population unless otherwise specified. Percentages will be rounded to 1 decimal place, unless otherwise

specified. Therefore, there may be cases where for instance the total of the percentages does not exactly equal 100%. In case confidence intervals are provided, they will be shown with 1 decimal place.

The number of missing values will be calculated as difference of the total number of subjects in the study population minus the number of non-missing values.

All p-values will be displayed to four decimals and rounded using standard scientific notation (e.g., 0.XXXX). If a p-value less than 0.0001 occurs it will be shown in tables as <0.0001.

All collected data will be presented in listings. Data not subject to analysis according to this plan will not appear in any tables or graphs but will be included only in the data listings.

4.2. Interim Analysis and Data Monitoring

[figure not shown]
No interim analyses are planned.

An Independent Data Monitoring Committee (iDMC) has overall responsibility for safeguarding the interests of subjects by monitoring relevant data obtained in the study and making appropriate recommendations based on the reported data, thus ensuring that the study is being conducted with the highest scientific and ethical standards.

5. Analysis Sets

The following analysis populations are planned for this study:

- **Enrolled Analysis Set:** The Enrolled Population Analysis Set includes all patients who sign the informed consent form including screen failures. This population will be used only for the purpose of describing patient disposition and for protocol deviations (note: screen failures will be excluded in protocol deviation outputs).
- All Treated Analysis Set: The All Treated Analysis Set includes all patients who receive any part of an infusion of study drug. The All Treated Analysis Set will be the primary population for efficacy endpoints, and will be used for safety and PK/PD endpoints.
- Evaluable Analysis Set: The Evaluable Analysis Set includes all patients in the All Treated Analysis Set who have
 - Received a minimum of 3 consecutive infusions of emapalumab, not more than 6 days between infusions,
 - Not had a diagnosis of secondary HLH subsequent to the initiation of emapalumab treatment.
- Evaluable Analysis Set Without Major Protocol Deviations: The Evaluable Analysis Set Without Major Protocol Deviations includes all patients in the Evaluable analysis set who do not have a major protocol deviation that is deemed to have an impact on the statistical analysis.

Inclusion in the analysis sets defined above will be determined at a data review meeting before database lock.

6. General Issues for Statistical Analysis

6.1. Statistical Definitions and Algorithms

6.1.1. Baseline

The last observation recorded prior to the first dose of emapalumab will be used as the baseline observation for all calculations of change from baseline.

6.1.2. Adjustments for Covariates

Not applicable.

6.1.3. Multiple Comparisons

Not applicable.

6.1.4. Handling of Dropouts or Missing Data

[figure not shown]
While all possible efforts will be made to ensure that patients stay in the study and all data is collected as scheduled, the occurrence of missing data cannot be completely eliminated.

Rules for handling missing or partial AEs or birth dates are described in Section 6.1.10

For defining the primary efficacy endpoint (Overall Response, see Section 6.1.9.4 for definition), values of some parameters may be missing, thus impacting the response assessment. Imputation rules for assessing disease response at EOT or Week 8 (whichever occurs earlier) and throughout the study have been pre-defined as follows. Note: Imputed values will be flagged in the listings for all endpoints where applicable.

Response at EOT or Week 8 (whichever occurs earlier):

- Missing data at EOT/Week 8 for the parameters relevant to assessment of Overall Response will be imputed by the closest available value from the EOT/Week 8 target day (as per Table 1 and Table 2) up to 8 days, provided upper window limit is before start of conditioning. For body temperature, in the event of repeated measures recorded on the same study day, the highest value will be selected.
- No imputation will be applied if no value is available within the time of the EOT/Week 8 target day up to 8 days. That parameter will be viewed as missing and complete response will not be assigned, even if all other parameters are normal.
- Values recorded at both scheduled and unscheduled visits will be considered.

• If all parameters are unable to be imputed then the overall response assessment will be recorded as missing.

Response throughout the study:

- For secondary time to event analyses (e.g., duration of response, time to response), both scheduled and unscheduled visits will be used for assessment of response.
- If a numerical parameter (i.e. Body Temperature, D-Dimer, Fibrinogen, Ferritin, Platelets, Neutrophils) needed for the response assessment is missing, the midpoint approach will be used to estimate the missing value i.e., the last observed value before the missing period will be averaged with the first value available after the missing period. This rule will be applied to parameter values missing for a period of up to a maximum of 7 consecutive days.

If a character parameter needed for the response assessment (i.e. Spleen Assessment, CNS) is missing, last observation carried forward method will be used to estimate the missing value - i.e., the last observed value within a maximum of 7 consecutive days before the missing period will be used.

In case that, after imputation, data is still missing in any of the criteria considered for the definition of response, a Complete Response cannot be adjudicated.

[figure not shown]
- If the maintenance of response (of at least 4 days) cannot be confirmed due to missing data, the response will be assumed to be lost. In case of calculation of duration of response (i.e. durability of first response) the next response period will be considered. If none of the subject's responses could have been confirmed to last for at least 4 days or only one response was documented which could not have been confirmed to last for at least 4 days, the duration of response will be set to 1 day applying a conservative imputation strategy.
- Since data relevant to CNS assessment has been collected at irregular time-points (based on individual patient conditions), the investigators assessment of CNS status will be carried-forward until the time-points of relevance for response analysis

For descriptive statistics on the evolution over time of clinical signs characterizing HLH disease, the time windows listed in Table 1 and Table 2 will be applied in the case that a parameter is not available on the specified study day.

For any assessment, if there is more than one observation during the visit window, the closest value (within the visit window) to the target day will be chosen first. In the case that there are 2 equidistant values to the study day of interest, the observation that is after the study day in question will be selected.

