- fever will only be reported when not linked to an identified cause (fever of unknown origin). If fever is considered as a sign of a confirmed infection or of HLH worsening or reactivation, it will not be reported as `fever`, but the cause will be reported as an AE;
- viral load positivity, in particular for Epstein-Barr virus (EBV), cytomegalovirus (CMV) and adenovirus, and evolution will be collected on a dedicated electronic Case Report Form (eCRF) module.
- Active infections will be reported as AEs, indicating whether constituting a primary infection or a reactivation (whenever possible). Pathogen positivity and evolution will be collected in a dedicated eCRF module.
- expected effects of conditioning (i.e., pancytopenia during conditioning and until engraftment) will not be reported as AEs

Any serious adverse event (SAE) that occurs during the course of the study, and regardless of causality to the study drug, must be notified by

the Investigator to Swedish Orphan Biovitrum AG, by fax or electronic transmission, within 24 hours of awareness, with the exception of:

- elective hospitalizations for surgical procedures that are a result of patient's pre-existing condition(s) which have not worsened during the study;
- hospitalizations required for emapalumab infusion and study visits (including a possible hospital stay overnight, if due to logistic convenience);
- hospitalizations post-HSCT lasting less than 72 hours and not leading to a new diagnosis, but triggered by a sign which will be reported as an AE. If a new diagnosis is found, it will be reported as an SAE.

After elimination of emapalumab only SAEs will be reported.

There are no predefined rules for permanent study drug discontinuation based on the current safety profile of the drug. An independent Data Monitoring Committee (iDMC) will be formed to ensure that any emergent safety concern will be timely assessed and appropriate measure taken for the patients, if relevant. Moreover, iDMC will be specifically tasked with regular assessment of extent of benefit and fatal events prior to transplant in treatment-naïve subgroup of patients.

A patient, his/her representative or the Investigator can decide at any time to prematurely discontinue treatment or to withdraw a patient from the study. This decision will have no impact on the patient's care.

A patient who prematurely discontinues treatment will receive alternative HLH therapy, according to the standard of care at the site.

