8 OUTLINE OF STUDY PROCEDURES

Patients will be recruited from specialized study sites, equipped with an intensive care unit and access to a bone marrow transplant unit.

Patients will be in the treating unit the day before the first administration of emapalumab (Study Day minus one, SD-1).

For a detailed description of the schedule of visits and assessments, refer to the Schedule of Assessment Table 1 (Screening and Treatment Period) and Table 2 (Follow-up Period).

Informed consent form must be signed by the patient or his/her legally authorized representative prior to any study-related procedures, with the assent of patients who are deemed suitable to provide it.

During the emapalumab treatment period, visits for infusion and efficacy/safety assessments will occur on SD0, SD3 and twice-a-week thereafter (not more than 4 days apart). In the circumstances when HSCT is scheduled beyond 12 weeks from emapalumab initiation and Complete Response is maintained (see Section 5.3), the treatment with emapalumab may continue once a week; acceptable time-window for visits in this case will be ± 1 day. An EOT visit has to be performed 3 ± 1 days after last emapalumab infusion.

Furthermore, during the follow-up period, the following time-windows are allowed around visits:

- Pre-conditioning: can be combined with EOT visit provided the two visits are

not more than 2 days apart

Week (Wk) 1-2-3, D+30 post-HSCT: ±2 days
 D+60, D+100 post-HSCT: ±1 week
 6-mo, 1-yr post-HSCT: ±4 weeks

If HSCT is not performed, the described schedule applies to the follow-up visits required to occur after the last emapalumab infusion.

Following windows can be applied to the vital signs measurement:

When measured every 15 minutes: ±5 minutes
 When measured every 30 minutes: ±10 minutes

- When measured at 1 hour and 2 hours after infusion: \pm 15 minutes

Some procedures are not to be done systematically but only if clinically relevant. For example:

- ECG is mandatory at Screening and at EOT visits, however it should be done at any other timepoint during the study, if deemed appropriate.
- Brain magnetic resonance imaging (MRI) is mandatory at Screening only in case of CNS disease, but should be done at any other time-points during the study to monitor evolution or to confirm onset of CNS involvement, as clinically indicated.

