10.3 MANAGEMENT OF TREATMENT DISCONTINUATION

All patients who discontinue emapalumab treatment will be treated according to the standard care at the site. However, it is recommended they continue in the study for long-term follow-up monitoring.

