	Study Day 51	52	51	Day of last infusion of emapalumab - 1 day		
b) no EOT visit available	EOT / Week 8	57	Day of last infusion of emapalumab	Day of last infusion of emapalumab + 6 days		
	ЕОТ	Start day of last infusion *	Start day of last infusion *	End day of last infusion *		

Table 2: Treatment Visit Windows, treatment duration >= 8 weeks

Visit Name		Torget day	Analysis visit window				
		Target day	From SD	To SD			
Week 8 is not th	Week 8 is not the last week prior to EOT visit or last infusion (subsequent weeks (x to n))						
	Week x	Week (x*7) +1	Target day – 3 days	EOT visit – 1 day			
a) EOT visit available	EOT / Week 8	57	54	60			
EOT		EOT visit	EOT visit	EOT visit			
	Week x	Week (x*7) +1	Target day – 3 days	Day of last infusion of emapalumab – 1 day			
b) no EOT visit available	EOT / Week 8	57	54	60			
ЕОТ		Start day of last infusion *	Start day of last infusion *	End day of last infusion *			

* Start and End date of infusion are in most of the cases the same date.

If treatment duration was ≥ 8 weeks (i.e. ≥ 56 days) the visit within the analysis visit window of 54 and 60 days and closest to the target day will be assigned as EOT/Week 8 analysis visit.

- a) If an EOT visit was performed the day of EOT visit will be assigned as EOT visit prior to start of conditioning.
- b) If no EOT visit was performed the day of last infusion will be assigned as EOT visit prior to start of conditioning.

[figure not shown]

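### The window for imputing missing EOT/Week 8 response parameters closes at conditioning but not at the start of replacement HLH therapy

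*SAP*

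**What the plan says.** SAP section 6.1.4 sets the rule for the primary endpoint. A response parameter missing at EOT/Week 8 takes the closest available value from the target day "up to 8 days, provided upper window limit is before start of conditioning". If nothing is found "within the time of the EOT/Week 8 target day up to 8 days", the parameter stays missing and Complete Response cannot be assigned. Unscheduled data are eligible: "Values recorded at both scheduled and unscheduled visits will be considered".

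The target day comes from the tables in SAP section 6.1.5. It is the EOT visit if treatment lasted under 56 days and a visit took place, and the day of the last infusion if no visit took place. For treatment of 56 days or more it is generally day 57. In Table 2, where Week 8 is the last week and there is no EOT visit, the window itself runs to "Day of last infusion of emapalumab + 6 days". Protocol section 8 fixes the visit timing: "An EOT visit has to be performed 3 ± 1 days after last emapalumab infusion".

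On what follows early stopping, the Protocol Synopsis says: "A patient who prematurely discontinues treatment will receive alternative HLH therapy, according to the standard of care at the site". Section 10.3 agrees: "All patients who discontinue emapalumab treatment will be treated according to the standard care at the site". Sections 3.4 and 10.1.3 keep these patients in long-term follow-up, so their data continue to be collected.

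**The concern.** The conditioning proviso shows that the authors did not want response read under a later treatment. Replacement HLH therapy is the other foreseeable later treatment after emapalumab stops, and it has no matching limit in section 6.1.4, in the response definition (SAP Table 6) or in the primary analysis (SAP 8.1).

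If a parameter is missing at EOT and the next value was measured after a switch, the rule imports that value. Improvement in platelets, neutrophils, ferritin, fibrinogen, D-dimer or temperature on the new regimen would then count as response to emapalumab. Such an error would tend to favour the drug, in a single-arm trial whose only formal test is a count of responders.

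**Working it through.** **1. The plan's own figures.** SAP 3.2 and 8.1 give n=34, null rate 40%, assumed rate 65%, 85% power and an exact binomial test at one-sided 0.025. They give no count of patients who switch therapy with missing EOT data. The rejection boundary is not stated but follows from

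P(X ≥ r) = Σ C(n,k)·0.40^k·0.60^(n−k), summed over k = r to n, taking the smallest r with P ≤ 0.025.

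At n=34 this gives r=20, with exact power 0.8257 at a 65% rate. The stated 34 follows from the normal approximation, [(1.96·√(0.40·0.60) + 1.036·√(0.65·0.35))/0.25]² = 33.85. That mismatch with 85% is a separate matter and does not affect this point.

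**2. Reach of the window, read forward.**

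| Case | Target day | Window closes |
|---|---|---|
| Under 56 days, EOT visit on time | last infusion + 2 to 4 days | last infusion + 10 to 12 days |
| Under 56 days, no EOT visit | day of last infusion | last infusion + 8 days |
| Target day 57 | day 57 | day 57 + 8 = day 65 |

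**3. Whether data fall inside it.** If HSCT is not performed, the follow-up schedule runs from the last infusion (Protocol section 8). The Week 1 visit is then at day 7 ± 2, that is, days 5 to 9. Protocol Table 2 schedules vital signs, physical examination, CBC, coagulation and biochemistry there. Days 5 to 9 lie wholly inside a window closing on day 10 to 12 and mostly inside one closing on day 8. Unscheduled values add to this.

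**4. How classification can change.** HLH Improvement needs at least three abnormalities improved or normalized. Take a patient with two improved at EOT and a third parameter missing. A post-switch value for that third parameter makes the patient a responder. Left missing, it does not.

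**5. Effect on the test.**

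| n | Responders | One-sided exact p |
|---|---|---|
| 34 | 20 | 0.0205 |
| 34 | 19 | 0.0444 |
| 41 | 24 | 0.0126 |
| 41 | 23 | 0.0270 |

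At either sample size, one patient at the boundary decides the result.

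**6. Illustration under an assumption.** Suppose the true attributable rate is 40% and a fraction f of non-responders is wrongly credited. The apparent rate is 0.40 + 0.60·f, and the expected number credited at n=34 is 34·0.60·f.

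| f (assumed) | Apparent rate | Expected credited, n=34 | Type I error, n=34 | Type I error, n=41 |
|---|---|---|---|---|
| 0 | 0.400 | 0 | 0.0205 | 0.0126 |
| 2.5% | 0.415 | 0.51 | 0.0312 | 0.0207 |
| 5% | 0.430 | 1.02 | 0.0462 | 0.0327 |
| 10% | 0.460 | 2.04 | 0.0922 | 0.0732 |

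The documents do not say which row, if any, applies.

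**The case against.** The sponsor has several fair replies.

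- **The design already counts responses under other HLH therapy.** Protocol 6.3.5 allows add-on treatment with emapalumab, and the primary analysis keeps those patients as possible responders. This stands as a limit on the point: closing the window does not settle attribution in general. But emapalumab is still being given in that case. Nothing in the documents says that response to a regimen replacing it should count.
- **Sensitivity analyses 3 and 4 cover it.** Both treat patients given other HLH treatment as non-responders. SAP 10.9 defines concomitant medication from the first dose with no end at the last infusion, so replacement therapy is probably captured. Some doubt remains because Protocol 6.3.5 describes add-on use as concomitant with emapalumab. In any case the primary estimate and p-value are unchanged.
- **An adverse event may block the response.** Condition aggravated, the SAP's code for HLH reactivation, is in SAP Table 21. While present, it rules out Complete and Partial Response. HLH Improvement stays open.
- **The rule is narrow.** It acts only on missing parameters and takes the closest value. The direction is not written as plus 8, although the mention of an upper limit points forward. If it were two-sided, pre-infusion laboratory values 2 to 4 days before EOT would usually be nearer, though for equidistant values within a visit window section 6.1.4 says "the observation that is after the study day in question will be selected". With no EOT visit and under 56 days of treatment, the target is the last infusion day, when laboratory tests are scheduled anyway.

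A reader might also infer more than the documents support. The 20% drop-out figure is a sample-size allowance, not a rate of switching with missing EOT data. No passage says that early stopping is often for lack of efficacy. The Table 2 +6-day row applies only to treatment of at least 56 days, so it does not describe patients who stop well before Week 8. Nor is the EOT visit open-ended: the Protocol fixes it at 3 ± 1 days. A late visit is a deviation reviewable under SAP 7.2, and if classed as major it removes the patient in sensitivity analysis 5.

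**Conclusion.** The gap is real and follows from the text: conditioning closes the imputation window and replacement HLH therapy does not. It can act only when an EOT/Week 8 parameter is missing, replacement therapy has started, and the closest eligible value comes after that start. The 10-to-12-day reach is a worst case that assumes a forward window. The number of patients affected is not in the documents and is probably small.

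The documents do not support concluding that the primary result will be contaminated; they support only that the rule permits it. The point still merits a change because any resulting error would tend to favour emapalumab, because one patient at n=34 separates p=0.0205 from p=0.0444, and because the sensitivity analyses do not alter the primary test.

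Observed values from an on-time EOT visit are a different question. Such a visit may already follow a switch, but overriding a protocol-timed assessment is a debatable estimand choice and is not recommended here.

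**What to change.** 1. In SAP 6.1.4, change the proviso to: *provided the value is dated before the start of conditioning and before the first dose of any replacement HLH treatment (using the agents recorded as HLH treatment in the eCRF) started at or after the last emapalumab infusion*.
2. Apply the same limit when a value is selected within the Table 2 no-EOT +6-day window.
3. If no eligible value exists within the 8-day window, leave the parameter missing under the existing rule. Do not search back to older values.
4. Keep observed EOT values from on-time visits in the primary analysis.
5. State in SAP 8.1 that sensitivity analyses 3 and 4 include HLH therapy started after the last infusion and before the EOT/Week 8 value used.

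The cost is a revised clause, one sentence in 8.1 and a date comparison in programming. Sample size and alpha do not change. A few more parameters will be missing. Because SAP 8.1 divides by all treated patients, the response rate may be slightly lower.
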